Administrative interim analyses are planned for the study. The Sponsor's study team and Investigators will remain blinded to individual patient data during and after the administrative interim analyses. The first interim analysis will be performed by the Sponsor when 12 patients in Stratum 1 have completed 8 weeks in the study, and the second interim analysis will be performed when 30 patients have completed 8 weeks in the study. Interim analyses may be omitted or added at the discretion of the Sponsor to allow for long term planning, and to assess ending the study or either arm early, as described in the statistical analysis plan (SAP). See [Figure 1](#) for a schematic representation of the study design.

Stopping rules for each dosing interval arm and for the study are detailed in [Section 9.5.1](#).

After the ~~first~~ 3 doses, patients who have undetectable BK plasma viral load at 2 or more consecutive assessments at least 2 weeks apart will discontinue PSL infusions. If a patient's viral load becomes undetectable, such a patient may be followed every 14 days for study evaluations as per the Schedule of Activities ([Section 1.3](#)). No patients are permitted to receive a subsequent infusion of PSL if they develop new onset GVHD (\geq Stage 1; see Appendix 5, [Section 10.5](#)) or cytokine release syndrome (CRS) ($>$ Grade 2; see Appendix 6, [Section 10.6](#)) at the proposed time for infusion of any subsequent dose.

An independent Data and Safety Monitoring Board (DSMB) will be convened for this study to routinely monitor patient safety and evaluate prespecified interim analyses to stop the study early (see [Section 10.1.5](#)).

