4.2 Scientific Rationale for Study Design

Even with the best current treatments (principally immunosuppression reduction), many centers report allograft nephropathy, rejection, and graft failure more commonly in patients with BK viremia than in those without ([Favi 2019](#), [El-Husseini 2019](#), [Sawinski 2015](#)). The unmet medical need in BK virus nephropathy is reflected in the continued use of (ineffective) antiviral treatments such as leflunomide, cidofovir, intravenous immunoglobulin G, and levofloxacin concurrently with immunosuppression reduction ([Bruminhent 2019](#)).

PSL multivirus-specific T cells target BK virus infected cells, and thus offer a way to lower viral load in BK viremic kidney transplant recipients at risk for BK nephropathy. To date, immunosuppression reduction is the only therapy that has succeeded in lowering BK viral load, and even it has had limited success and can lead to increased risk of rejection and/or production of donor-specific antibodies. This proof-of-concept study will also identify the dosing interval for virus-specific T cell infusions needed to lower viral load in kidney transplant recipients on continued immunosuppression and potentially limit the damage caused by BK virus replication in the kidney allograft.

The use of placebo in this clinical study is justified for the following reasons:

- 1) A placebo control group is required to provide an objective, contemporaneous assessment of the therapeutic effects and AE profile of PSL.
- 2) The use of an active control group in the study is not feasible since there are no approved, efficacious antiviral therapies for the treatment of BKV infections.

3) Investigators are permitted to administer standard of care immunosuppression reduction as per the algorithm included in Appendix 7 ([Section 10.7](#)).

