9.4.5 Safety Analysis

All safety data will be summarized by treatment arm actually received. Categorical endpoints will be summarized using number and percentage of patients within each category. Continuous endpoints will be summarized descriptively with summary statistics (number, mean, standard deviation, standard error, median, first quartile, third quartile, minimum, and maximum).

Adverse events will be coded using the Medical Dictionary for Regulatory Activities. A TEAE is defined as an AE with a start date and time on or after the first dose of study treatment and through the Week 24 visit. Treatment-emergent AEs will be summarized by System Organ Class and Preferred Term and further by severity (according to the National Cancer Institute [NCI] Common Terminology Criteria for Adverse Events [CTCAE] v5.0) and relationship to study treatment. The incidence of SAEs will be summarized.

The incidence of AESIs including acute GVHD, CRS, infusion reactions and their corresponding exact binomial confidence intervals with 95% confidence level will be presented by treatment group. Grading criteria for GVHD and CRS are in Appendix 5 in [Section 10.5](#) and Appendix 6 in [Section 10.6](#), respectively.

Descriptive statistics will be provided for relevant laboratory, vital sign, and ECG data. Abnormal laboratory results will be graded according to NCI CTCAE v5.0, if applicable. A shift table, presenting the 2-way frequency tabulation for baseline and the worst post-baseline value according to the NCI CTCAE grade, will be provided for selected clinical laboratory tests.

Clinical safety laboratory parameters will be presented in summary tables. Changes from baseline in laboratory parameters, vital sign parameters, and quantitative ECG parameters will be summarized. Selected laboratory parameters will be summarized in shift tables.

Statistical comparisons will be carried out using Fisher's exact test and Student's t test. A 1-sided $P < .05$ will be considered statistically significant. Key secondary outcomes such as BK viral load assessments and change in eGFR (measured by comparing the slope of decline in the eGFR over time) between the placebo group and treatment group will be analyzed using the statistical comparisons described above. The baseline demographics of patients, such as age and gender, etc., will also be analyzed to ensure adequate randomization.

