9.5 Interim Analyses

Administrative interim analyses are planned for the study. The Sponsor's study team and Investigators will remain blinded to individual patient data during and after the administrative interim analyses. All administrative interim analyses will be conducted by the Sponsor.

- The first administrative interim analysis will be performed by the Sponsor when 12 patients in Stratum 1 [REDACTED] have completed 8 weeks in the study.
- The second administrative interim analysis will be performed when 30 patients have completed 8 weeks in the study.
- Interim analyses may be omitted or added at the discretion of the Sponsor to allow for long term planning, and to assess ending the study or either arm early.

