After the first 3 doses, patients who have undetectable BK plasma viral load at 2 or more consecutive assessments at least 2 weeks apart will discontinue PSL infusions. If a patient's viral load becomes undetectable, such a patient may be followed every 14 days for study evaluations as per the Schedule of Activities. Patients will not be permitted to receive a subsequent infusion of PSL if they develop new onset graft vs host disease (GVHD) \geq Stage 1 or cytokine release syndrome (CRS) > Grade 2 at the proposed time for infusion of any subsequent dose.

A summary of study design is shown in [Figure 1](#).

2.2.2 *Study Drug*

PSL is a third-party, donor-derived, "off-the-shelf," virus-specific T cell product with specificity for BKV, AdV, CMV, EBV, and HHV-6 (with additional cross-reactive specificity for JCV) that is cryopreserved and ready for immediate use. Cryopreservation media (without cells) will serve as the placebo and will be identical in volume and appearance when administered.

2.2.3 *Sample Size Determination*

No formal sample size determination was made for this study, whose primary endpoint is safety and tolerability. Approximately 60 patients will be randomized at approximately 38 clinical sites. Patients (n=20 in each arm) will be randomized to receive PSL (administered at a dose interval of every 14 or 28 days after 3 initial weekly doses) or placebo.

Patients will be stratified [REDACTED]

[REDACTED] A minimum of 6 patients must be enrolled in each stratum, but the remaining patients can be enrolled in either stratum.

Figure 1. Study Flow Chart

b Administrative interim analysis #1 will be performed by the Sponsor when 12 patients in Stratum 1 have completed 8 weeks in the study. Administrative interim analysis #2 will be performed when 30 patients have completed 8 weeks in the study. Interim analyses may be omitted or added at the discretion of the Sponsor to allow for long term planning, and to assess ending the study or either arm early.

Abbreviations: BKV=BK virus; Q=every; S/P=status post

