3.5 Safety Analyses

Safety data will be summarized by treatment group (i.e., PSL, Placebo and Overall). Safety summary tables will be generated for actual treatment received, based on the Safety Population. The primary objective of the study is to assess the safety and tolerability of PSL in kidney transplant recipients based on TEAEs and changes in vital signs, physical examinations, clinical laboratory assessments, and ECGs. Categorical endpoints will be summarized using the number and percentage of patients within each category. Continuous endpoints will be summarized descriptively with summary statistics (number, mean, standard deviation, standard error, median, first quartile, third quartile, minimum, and maximum).

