3.5.1 Adverse Events

All AEs will be coded to system organ class and preferred term using MedDRA. TEAEs are defined as AEs with a start date and time on or after the first dose of study treatment through

the end of the study. Adverse events of special interest (AESI) include infusion-related AEs, GVHD (graft versus host disease), and CRS (cytokine release syndrome).

An overall summary of AEs will be produced for the following by treatment group. The numbers and percentages of patients will be provided for the following:

- Any TEAEs
- Any TEAEs by severity
- Any treatment-related TEAEs
- Any TEAEs of special interest (AESIs): graft versus host disease, infusion reaction and/or cytokine release syndrome.
- Any treatment-related TEAESIs
- Any serious AEs (SAEs)
- Any treatment-emergent serious AEs (TESAEs)
- Any treatment-related TESAEs
- Any TEAEs leading to discontinuation of study treatment
- Any TEAEs leading to discontinuation of study
- Any TEAEs leading to death

The summaries of above TEAE categories by system organ class (SOC) and preferred term (PT). In addition, TEAE and TESAEs will be summarized by PT (descending frequency). TEAEs, TESAEs, and TEAESIs will also be summarized by severity.

Patients with multiple AEs will be counted only once per SOC and PT. The number and percentage of patients with TEAEs will be tabulated by the highest CTCAE Grade.

Listings will be presented for all AEs, any deaths, SAEs, AESI, and TEAEs leading to discontinuation of study treatment and study.

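### SAP 3.5 puts both posoleucel (PSL) dosing-interval arms into one safety column and omits the AESI confidence intervals that protocol 9.4.5 promises

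*SAP*

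**What the plan says.** Protocol 9.4.5 makes two commitments. The first is "All safety data will be summarized by treatment arm actually received". The second covers the incidence of acute GVHD, CRS and infusion reactions, for which "their corresponding exact binomial confidence intervals with 95% confidence level will be presented by treatment group".

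SAP 3.5 sets the columns for safety: "Safety data will be summarized by treatment group (i.e., PSL, Placebo and Overall"). For categorical safety data it plans counts and percentages. SAP 3.5.1 does the same for the overall adverse event summary, AESIs included: "The numbers and percentages of patients will be provided for the following".

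SAP 2.2.1 describes three arms. SAP 2.2.3 gives 20 patients per arm and describes PSL as "administered at a dose interval of every 14 or 28 days after 3 initial weekly doses", so two of the three arms are PSL arms that differ in dosing interval.

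**The concern.** The SAP departs from the protocol on the primary endpoint in two ways and gives a reason for neither: the PSL arms share one column, and the AESI intervals are absent.

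The interval is the design variable of this trial. Both PSL arms use the same cell dose, and placebo infusions fill the schedule to keep the blind (footnote 17 of the Schedule of Activities). Over the same 12 weeks, the longer interval therefore means fewer active infusions. One PSL column averages over that difference in exposure, and a reader who wants to know whether tolerability varies with interval would have to recount events from listings.

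The protocol also contemplates acting on single arms. Section 4.1 states "Stopping rules for each dosing interval arm and for the study are detailed in" Section 9.5.1, and Section 9.5 allows interim analyses "to assess ending the study or either arm early".

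GVHD and CRS are described as theoretical risks, so few or no events may be seen. In that case the upper confidence limit is the informative result, because it states which rates the data exclude.

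**Working it through.** The documents give no AESI rate, interval width or power for safety, so there is no stated figure to reproduce. The check is a comparison of texts, followed by an illustration of scale.

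**Columns.** Protocol 9.4.5 says arm. SAP 3.5 lists PSL, Placebo and Overall after i.e., which introduces a definition and not an example. The general rule in SAP 3.1.4 (by treatment group and stratum) does not restore the arms, because 3.5 itself says what the groups are for safety. By contrast, the figures in SAP 3.4.1 and 3.4.2 for viral load, eGFR and creatinine are planned both with three separate arms and with the PSL arms combined. The by-arm layout is thus already in the SAP, but not for the safety tables.

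**Intervals.** The only confidence interval in the SAP is the 95% CI of the Kaplan-Meier median in 3.4.2. No AESI interval appears, either by arm or for pooled PSL.

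**Declared or not.** Where this SAP drops a planned analysis it says so: time to death and time to resolution of non-BK infections in 3.4.2, and biomarkers in 2.3.4. It makes no such statement for these two items.

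**Scale.** Inputs: n = 20 per arm (SAP 2.2.3), so pooled PSL has n = 20 + 20 = 40. Event counts are assumed.

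Formulas:
- Exact (Clopper-Pearson) 95% limits for x events in n: lower = the 0.025 quantile of Beta(x, n − x + 1), taken as 0 when x = 0; upper = the 0.975 quantile of Beta(x + 1, n − x).
- With x = 0 the upper limit reduces to 1 − 0.025^(1/n).
- One-sided Fisher p for x/20 against 0/20 = C(20, x) / C(40, x).

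Zero events: 1 − 0.025^(1/20) = 16.8% for one regimen; 1 − 0.025^(1/40) = 8.8% for pooled PSL.

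All events in one arm:

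| Split | Affected arm (95% CI) | Single PSL column | Exact 95% CI for that column (not planned) | Even split with the same print | One-sided Fisher p, arm v arm |
|---|---|---|---|---|---|
| 2/20 v 0/20 | 10% (1.2–31.7%) | 2/40 = 5% | 0.6–16.9% | 1 + 1 | 190/780 = 0.244 |
| 4/20 v 0/20 | 20% (5.7–43.7%) | 4/40 = 10% | 2.8–23.7% | 2 + 2 | 4,845/91,390 = 0.053 |
| 6/20 v 0/20 | 30% (11.9–54.3%) | 6/40 = 15% | 5.7–29.8% | 3 + 3 | 38,760/3,838,380 = 0.010 |

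The chance of seeing at least one event when the true rate is 5% is 1 − 0.95^20 = 64% in one arm and 1 − 0.95^40 = 87% in pooled PSL. An arm with no events is thus weak evidence without its interval.

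**The case against.** The strongest reply is that the SAP's columns match the stated objectives. The primary objective compares PSL with placebo, and the regimen objective concerns efficacy only. Protocol 4.2 says "This proof-of-concept study will also identify the dosing interval for virus-specific T cell infusions", but the sentence goes on to tie that aim to lowering viral load. This stands: the sentence does not by itself create a need for by-arm safety tables. The case for them rests on the by-arm wording of protocol 9.4.5 and on a title and design that describe a multiple-dosing-interval study of safety and tolerability.

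Second, decisions to stop an arm need not use these tables. The DSMB has its own charter and an unblinded statistician, and Section 9.5.1 as it reads holds only individual-patient and study-wide rules. This also stands: nothing shows that live monitoring is impaired. The gap is in the planned final tables.

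Third, the protocol uses its terms loosely. The phrase about treatment arm could be read mainly as an as-treated rule, which SAP 3.5 keeps, and the AESI sentence says group. That is a possible reading of the first sentence, though not the natural one in a three-arm trial. It does mean that intervals for pooled PSL and placebo would satisfy the second sentence. The SAP provides not even those.

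Fourth, the practical loss is limited. AE, SAE and AESI listings are planned, and an exact interval can be worked out from any printed count and denominator. The splits above are assumed and extreme, and by-arm comparisons at n = 20 are weak: even 4 against 0 gives p = 0.053. All of this is true. It limits the severity but leaves the departure from the protocol unexplained.

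**Conclusion.** The point holds on both counts. SAP 3.5 replaces the protocol's by-arm safety summaries with a single PSL column, and the SAP omits the exact AESI intervals, in each case without a stated reason. As written, the AE, AESI, laboratory, vital-sign and ECG summary tables cannot distinguish the regimens. A zero AESI count would appear without its upper limit, which is 16.8% for one regimen and 8.8% for pooled PSL. These figures rest on the planned 20 patients per arm, and the non-zero illustrations also on assumed counts. The matter should be fixed, but it is a gap in descriptive reporting: pooled PSL against placebo answers the primary objective, and the patient-level data are kept.

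**What to change.** In SAP 3.5 and 3.5.1 to 3.5.4, define the safety columns as each PSL arm, pooled PSL and placebo, with Overall optional, all by treatment actually received. In 3.5.1, add the exact (Clopper-Pearson) 95% interval for acute GVHD, CRS and infusion reactions. Intervals for pooled PSL and placebo are the least that protocol 9.4.5 requires; showing them for each arm as well is a recommendation beyond its wording. State that by-arm safety results are descriptive. If the sponsor prefers to pool, the SAP should record and justify the departure from protocol 9.4.5.

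The cost is SAP and table-shell wording, one or two extra columns and one interval line per AESI. No new data are needed. The drawbacks are wider tables and sparse by-arm counts that must not be over-read.

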3.5.1 Adverse Events

All AEs will be coded to system organ class and preferred term using MedDRA. TEAEs are defined as AEs with a start date and time on or after the first dose of study treatment through

the end of the study. Adverse events of special interest (AESI) include infusion-related AEs, GVHD (graft versus host disease), and CRS (cytokine release syndrome).

An overall summary of AEs will be produced for the following by treatment group. The numbers and percentages of patients will be provided for the following:

- Any TEAEs
- Any TEAEs by severity
- Any treatment-related TEAEs
- Any TEAEs of special interest (AESIs): graft versus host disease, infusion reaction and/or cytokine release syndrome.
- Any treatment-related TEAESIs
- Any serious AEs (SAEs)
- Any treatment-emergent serious AEs (TESAEs)
- Any treatment-related TESAEs
- Any TEAEs leading to discontinuation of study treatment
- Any TEAEs leading to discontinuation of study
- Any TEAEs leading to death

The summaries of above TEAE categories by system organ class (SOC) and preferred term (PT). In addition, TEAE and TESAEs will be summarized by PT (descending frequency). TEAEs, TESAEs, and TEAESIs will also be summarized by severity.

Patients with multiple AEs will be counted only once per SOC and PT. The number and percentage of patients with TEAEs will be tabulated by the highest CTCAE Grade.

Listings will be presented for all AEs, any deaths, SAEs, AESI, and TEAEs leading to discontinuation of study treatment and study.

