2.2 Study Design

2.2.1 Overview

This is a Phase 2, multicenter, randomized, double-blind, placebo-controlled, multiple dosing interval, 2-period study of the safety, tolerability and efficacy of adoptively transferred PSL virus-specific T cells in kidney transplant recipients with BK viremia.

This study is comprised of 2 periods. Period 1 includes a 2-week window for screening assessments followed by a 12-week treatment period for eligible patients. Period 2 (consists of a 12-week) follow-up. Overall, the total duration of patient participation in the study is approximately 26 weeks (2 weeks for screening, 12 weeks of treatment, and 12 weeks of follow-up).

Patients who meet all of the inclusion criteria and none of the exclusion criteria will be enrolled into the study and randomized to receive PSL or placebo infusions. Patients will be stratifie [REDACTED]

[REDACTED] atients will be monitored following randomization for safety, BK viral load, renal function, and immune function, including modification of immunosuppression reduction. Patients will be monitored following randomization for safety, BK viral load, renal function, and immune function, including modification of immunosuppression reduction.

Patients will receive infusions of either PSL or placebo for 12 weeks. [REDACTED]

[REDACTED] All infusions will be administered IV (via peripheral or central line) over approximately [REDACTED] as a slow push. Patients will receive the same dose for all infusions.

The study will consist of 3 treatment arms. To maintain the blind, all patients will receive an infusion (either PSL or placebo) weekly for the first 3 weeks of the dosing period, followed by every other week dosing for the remaining 9 weeks. The treatment arms and associated infusions are as follows:

[REDACTED]

Administrative interim analyses are planned for the study as described in Section 3.7. The Sponsor's study team and Investigators will remain blinded to individual patient data during and after the administrative interim analyses.

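### Per-patient counts of infusion-related AEs dilute an excess risk per infusion when infusions stop on viral clearance; add a comparison over the first 3 infusions

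*SAP*

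**What the plan says.** SAP 2.1.1 makes the comparison of safety and tolerability between PSL and placebo the primary objective. SAP 2.3.5 names infusion-related AEs, GVHD and CRS as the events of special interest.

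For these events SAP 3.5.1 counts patients: "The numbers and percentages of patients will be provided for the following", and one item in that list is "Any TEAEs of special interest (AESIs): graft versus host disease, infusion reaction and/or cytokine release syndrome". Repeat events drop out: "Patients with multiple AEs will be counted only once per SOC and PT". SAP 3.5 gives the safety groups as PSL, Placebo and Overall, so both PSL regimens share one heading. Protocol 9.4.5 adds exact binomial intervals by group, which are also per-patient proportions.

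On exposure, SAP 2.2.1 schedules blinded infusions "weekly for the first 3 weeks of the dosing period, followed by every other week dosing for the remaining 9 weeks". The schedule of activities shows 8 infusion visits: Day 1 and Weeks 1, 2, 4, 6, 8, 10 and 12. Once three doses have been given, a response rule applies: "patients who have undetectable BK plasma viral load at 2 or more consecutive assessments at least 2 weeks apart will discontinue PSL infusions". SAP 2.2.3 gives the PSL interval after the 3 weekly doses as 14 or 28 days, and the schedule footnotes provide for placebo infusions to keep the blind. The 28-day arm therefore receives some infusions without cells.

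SAP 3.3.7 summarizes duration, number of doses and total dosing. For patients who stop because viremia resolved, it calculates planned volume only up to the last dosing date. Neither document plans a rate per infusion, a table by infusion number or a comparison over a common number of infusions.

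**The concern.** An infusion reaction can occur only when an infusion is given. From the fourth infusion on, the number given depends on viral response, which PSL is meant to improve. If PSL works, PSL patients have fewer occasions for a reaction than placebo patients, and a count of patients with at least one reaction then moves in favour of PSL for a reason unrelated to how well an infusion is tolerated. Cell-free infusions in the 28-day arm, counted under PSL, push the same way.

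Infusion-related AEs are a named component of the primary safety comparison. A reader of the planned tables could see fewer doses on PSL but would have no exposure-matched figure to set beside the patient counts. The compliance figure would not show the shortfall either, because its denominator is cut at the last dose for responders.

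**Working it through.** **Plan's own figures.** There is no power, reaction rate, clearance rate or expected number of infusions to reproduce. The stated size is consistent: 3 arms × 20 = 60, so 40 PSL against 20 placebo.

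**From the documents.** Up to 8 infusions per patient. No response-driven stop before the third dose. The first post-baseline BK loads are at Weeks 2 and 4, so the earliest stop falls after about 3 to 5 infusions, depending on result turnaround and on how the rule is read.

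**Assumed (not in the documents).**
- Reaction risk is 6% per PSL infusion and 4% per cell-free infusion (true ratio 1.5), constant and independent.
- The 28-day arm receives PSL at infusions 1, 2, 3, 5 and 7 and cell-free infusions at 4, 6 and 8.
- A share f of PSL patients and g of placebo patients stop after k infusions; the rest receive all 8. The stop applies to blinded infusions in every arm.

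**Formula.** The chance of at least one reaction in n infusions is 1 − 0.94^a × 0.96^b, with a PSL and b cell-free infusions and a + b = n. Arm incidence = f × (value at k) + (1 − f) × (value at 8), with g in place of f for placebo. Pooled PSL is the mean of the two equal-sized arms.

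| Infusions received | 14-day arm | 28-day arm | Placebo |
|---|---|---|---|
| 4 | 21.9% | 20.3% | 15.1% |
| 5 | 26.6% | 25.0% | 18.5% |
| 6 | 31.0% | 28.0% | 21.7% |
| 8 | 39.0% | 35.1% | 27.9% |

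**What the planned table would show (true ratio per infusion 1.5).**

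| PSL stopping | Placebo stopping | Pooled PSL | Placebo | Ratio |
|---|---|---|---|---|
| none | none | 37.1% | 27.9% | 1.33 |
| 25% after 4 | none | 33.1% | 27.9% | 1.19 |
| 25% after 6 | 10% after 6 | 35.2% | 27.2% | 1.29 |
| 50% after 4 | none | 29.1% | 27.9% | 1.04 |
| 50% after 5 | none | 31.4% | 27.9% | 1.13 |
| 50% after 6 | 10% after 6 | 33.3% | 27.2% | 1.22 |
| 75% after 4 | none | 25.1% | 27.9% | 0.90 |
| 75% after 6 | 10% after 6 | 31.4% | 27.2% | 1.15 |

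**First 3 infusions only.** 1 − 0.94³ = 16.9% against 1 − 0.96³ = 11.5%, ratio 1.47.

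**Where the loss from 1.5 comes from.** Counting patients once over 8 infusions gives 39.0/27.9 = 1.40 in the 14-day arm. Pooling with the 28-day arm lowers this to 1.33. Only the fall below 1.33 is due to response-driven stopping. If the 28-day arm instead received 6 PSL and 2 cell-free infusions, its incidence would be 1 − 0.94⁶ × 0.96² = 36.4%, and the no-stopping ratio (39.0 + 36.4)/2/27.9 = 1.35.

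**Equal risk.** With 5% per infusion in every arm, half of PSL patients stopping after 4 and no placebo stops: PSL 0.5 × (1 − 0.95⁴) + 0.5 × (1 − 0.95⁸) = 0.5 × 18.5% + 0.5 × 33.7% = 26.1%, against 33.7% on placebo.

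**Larger excess.** With 4% against 2% per infusion, all PSL infusions active, half of PSL stopping after 5 and no placebo stops, the table shows 23.2% against 14.9% (ratio 1.55); with 8 infusions for everyone it shows 27.9% against 14.9% (1.87). The difference vanishes only if about 79% of PSL patients stop after 3 infusions or nearly all stop after 4.

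**The case against.** The strongest reply is that per-patient incidence is a proper measure. Stopping on clearance is part of the regimen, so the risk to a patient assigned that regimen is a legitimate randomized comparison. That stands: the table should stay, and what is missing is a second measure.

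Second, the sharpest figures rest on unfavourable assumptions. A stop after 4 infusions needs undetectable loads at Weeks 2 and 4. The Week 2 sample is drawn before that visit's infusion, so clearance would have to follow two infusions, with entry loads allowed up to 10,000,000 copies/mL. Some clearance on placebo is plausible, since entry starts at 350 copies/mL against an LLOQ of 156 and immunosuppression reduction is permitted in all arms. This also stands, and it is why a range is given.

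Third, a reader might infer that any real excess could vanish, or that the primary safety conclusion could point the wrong way. The documents do not support that. A doubling is usually diluted and remains visible. For a true ratio of 1.5, the reversal shown above needs three quarters of PSL patients stopping at 4 infusions. The 26% against 34% under equal risk is a gap of about 8 points with a standard error near 13 points: √(0.261 × 0.739/40 + 0.337 × 0.663/20) = 0.126. The primary endpoint is a qualitative assessment of all TEAEs, vital signs, examinations, laboratory tests and ECGs (Protocol 9.4.2), and Protocol 9.1 plans no formal test.

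Fourth, doses are summarized, AESIs are listed by patient and reviewed by the DSMB, and tables by preferred term would partly separate the event types. These outputs let a reader notice unequal exposure, but none adjusts for it.

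Last, per-infusion rates have their own bias: infusions after the third go to patients who have not cleared virus and have not met a safety stop. That stands and limits the per-infusion table to description.

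**Conclusion.** The point holds as one of dilution. SAP 3.5.1 has no equal-exposure summary of infusion-related AEs, although exposure after the third infusion depends on response and part of the 28-day arm's exposure is cell-free. If PSL clears virus more often than placebo, the per-patient comparison shifts toward PSL, and a modest excess per infusion can disappear.

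For an assumed true ratio of 1.5, the displayed ratio is 1.33 with no early stopping, about 1.19 to 1.29 if a quarter of PSL patients stop after 4 to 6 infusions, and about 1.04 to 1.22 if half do, with 0 to 10% of placebo patients stopping. Over the first 3 infusions it is 1.47. All these figures rest on assumed reaction, clearance and stopping rates. Reactions concentrated in the first 3 infusions would be diluted less than the constant-risk model suggests.

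With 40 against 20 patients, precision is low whichever measure is used, so unequal exposure is one of several reasons a signal could be missed. The addition is worth making because it is nearly free and concerns the primary objective.

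**What to change.** Keep the whole-study per-patient table in SAP 3.5.1 and describe it as the regimen-level measure. Add two tables.

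- **(a) First 3 infusions.** Patients with an infusion-related AE during the first 3 infusions, by randomized regimen and placebo, separate from GVHD and CRS, with exact binomial intervals. All arms have the same planned number of infusions here ("all patients will receive an infusion (either PSL or placebo) weekly for the first 3 weeks of the dosing period") and no response-driven stop has yet applied, so this is the equal-exposure randomized comparison.
- **(b) Per infusion, descriptive only.** Infusion-related AEs per infusion given, by infusion number and content (PSL, cell-free in a PSL arm, placebo), with intervals that treat the patient as a cluster. Add a note that infusions after the third go to a response-selected subset.

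State also how an event is attributed to a particular infusion.

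No new data are needed. Protocol 6.4 records the date and time of each dose given in the clinic, the TEAE definition uses start date and time, and the randomization codes held by the IRT vendor should identify infusion content. The cost is a few lines of SAP text and two tables. The drawback is that (b) is not a randomized comparison and must be labelled so.
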